#### PECS I-II Block Protocol:

With the patient in the supine position and the upper limb abducted 90°, the ultrasound (USG) probe is placed under the lateral third of the clavicle. After identifying the axillary artery and vein, the probe is aligned with the second rib. It is then moved inferolaterally to visualize the third rib and the pectoralis major, pectoralis minor, and serratus anterior muscles. A 10 cm block needle is advanced between the pectoralis major and minor muscles under ultrasound guidance. After confirming the site with 2–3 mL isotonic saline (hydrodissection), 10 mL of 0.25% bupivacaine is administered (PECS I). The probe is then moved toward the axilla, and when the serratus anterior muscle over the fourth and fifth ribs is visualized, another 20 mL of 0.25% bupivacaine is injected between the pectoralis minor and serratus anterior muscles (PECS II).

#### ESP Block Protocol:

The patient is placed in lateral decubitus position with the surgical side up. The ultrasound probe is placed longitudinally at the level of the T4–5 spinous processes and then moved laterally toward the surgical side. The transverse process and overlying trapezius, rhomboid, and erector spinae muscles are visualized. Under aseptic conditions, the block needle is inserted at a 30–40° crano-caudal angle, passing through the trapezius, rhomboid, and erector spinae muscles. After confirming placement with 2–3 mL isotonic saline, 20–30 mL of 0.25% bupivacaine is injected between the erector spinae muscle and transverse process.

Both PECS I-II and ESP blocks will be performed under ultrasound guidance, and the needle position will be verified through anatomical visualization and hydrodissection. Blocks will

be considered successful if applied by the responsible anesthesiologist under these conditions.

At the end of surgery, maintenance agents will be discontinued, and intravenous sugammadex will be administered to reverse muscle relaxation, dosed according to patient weight. About 30 minutes prior to the end of surgery, 1000 mg intravenous paracetamol will be routinely administered for analgesia. Extubation will occur after the patient regains spontaneous breathing and emerges from anesthesia. This is standard procedure and will not be modified for the study. No interference will occur with decisions regarding anesthesia drugs, ventilation methods, or intubation technique.

#### Postoperative Pain Control:

In addition to routine 3×1000 mg IV paracetamol, rescue analgesia with IV tramadol (0.5 mg/kg) will be administered as needed. These practices are part of our standard multimodal analgesia protocol and not specific to the study. After discharge, patients will be transitioned to oral paracetamol, with a recommendation of 3×500 mg daily for one month if necessary

Postoperative follow-up interviews will be conducted by a study assistant. Time of initial pain, and whether rescue analgesia was needed within the first 24 hours, will be recorded. Pain levels will be assessed at 20 minutes, 6 hours, and 1 day postoperatively using the Numerical Rating Scale (NRS). If NRS >0, the DN4 (Douleur Neuropathique 4) questionnaire will be administered. At the 3-month follow-up, patients will be contacted via phone and evaluated with the DN2 and SF-12 questionnaires. No blood samples or invasive procedures will be performed for research purposes.

The NRS is a simple and widely used 0–10 scale to assess pain severity, from "0 = no pain" to "10 = worst imaginable pain." It is considered valid and reliable. The DN4 questionnaire, administered by clinicians, includes 10 items to evaluate neuropathic pain, with a sensitivity of 83% and specificity of 90%. A score ≥4 indicates neuropathic pain. The SF-12 Quality of Life questionnaire, validated in Turkish, consists of 12 items and is used to assess overall health status and quality of life.

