Younger age (<40 years) has been identified as a major risk factor, though age does not appear to correlate with the intensity of reported pain (10). Severe acute postoperative pain is also considered a predictive factor for the development of chronic pain. Furthermore, radiotherapy to the breast and/or axillary region has been associated with an increased risk of chronic pain when compared to patients who did not receive radiation therapy (11). Among surgical contributors to PMPS, extensive axillary lymph node dissection is significant due to the increased risk of intercostobrachial nerve injury, which may lead to neuropathic pain (12,13).

Strategies aimed at reducing the risk of PMPS emphasize optimizing perioperative pain management. Techniques such as paravertebral, erector spinae plane (ESP), and pectoral

nerve blocks are routinely applied in appropriate surgical cases to reduce postoperative pain and minimize the risk of chronic pain development in many centers, including ours (14). Both ESP and PECS I-II blocks have demonstrated efficacy and are associated with low complication rates (14,15,16).

In our study, we aim to observe the incidence of chronic pain following mastectomy in patients who have received either a pectoral nerve block (PECS I-II) or an erector spinae plane (ESP) block as part of their pain management strategy. These blocks will be administered by the attending anesthesiologist after general anesthesia induction and prior to the initiation of surgery. The choice and timing of the block will be determined independently by the anesthesiologist and not influenced by the study team. The primary outcome of this study is to compare the incidence of chronic postoperative pain between the two groups. The secondary outcome is to assess the impact of these blocks on acute postoperative pain levels and opioid requirements.

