#### **3.5. Research Method and Data Collection Tools:**

Upon admission to the operating room, non-invasive arterial blood pressure, electrocardiogram, and peripheral oxygen saturation monitoring will be conducted before

the induction of general anesthesia. This is the routine monitoring protocol applied prior to anesthesia. All patients will receive standard general anesthesia and standard ventilation modes. The research team will not intervene in the anesthesia procedure.

According to the standard anesthesia practice in these cases, anesthesia induction is performed with propofol (1.5–2.5 mg/kg), rocuronium (0.4–0.6 mg/kg), and fentanyl (1–2 mcg/kg), with a 50% oxygen-air mixture. Standard ventilator settings are applied.

Anesthesia maintenance consists of 2% sevoflurane with 50% oxygen-air mixture. These practices are routine in our operating theater and are not specifically designed for this study. In the event of any non-routine requirement, decisions will be made by the responsible anesthesiologist, without any intervention from the research team. The study will commence after anesthesia induction and block application.

Following the induction of general anesthesia, the responsible anesthesiologist will independently administer either the PECS I-II or ESP block prior to surgical incision. The choice of block will not be influenced by the study and will be determined solely by the anesthesiologist, regardless of group distribution. The research team will not interfere in the selection or method of block administration.

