#### **3.6. Data Collection**

Following ethics committee approval, eligible patients aged 18–65 years scheduled for elective modified radical mastectomy between April 15 and May 15, 2024, at Hacettepe University Hospital, who had already been assigned ESP or PECS I-II blocks for postoperative pain control independent of the study, will be enrolled. The study is observational, and no interventions will be made regarding clinical treatment decisions. Patient demographic data (ASA score, age, sex, weight, height, BMI, comorbidities) and intraoperative details will be recorded

Postoperative data within the first 24 hours will be collected via face-to-face interviews and entered into the follow-up and DN4 forms. At 3 months, DN2 and SF-12 questionnaires will be administered via telephone interviews

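### No masking is described for the study assistant who interviews patients, although the primary outcome and the acute pain scores are patient reports obtained by interview

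*Combined protocol and SAP*

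**What the plan says.** Section 2 sets the outcomes: "The primary outcome of this study is to compare the incidence of chronic postoperative pain between the two groups" and "The secondary outcome is to assess the impact of these blocks on acute postoperative pain levels and opioid requirements".

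Collection is described twice. Section 3.5, under Postoperative Pain Control, says "Postoperative follow-up interviews will be conducted by a study assistant". It lists time of first pain, need for rescue analgesia, and NRS at 20 minutes, 6 hours and 1 day, with DN4 added when NRS is above 0. Section 3.6 says "Postoperative data within the first 24 hours will be collected via face-to-face interviews and entered into the follow-up and DN4 forms" and "At 3 months, DN2 and SF-12 questionnaires will be administered via telephone interviews".

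Two statements in section 3.5 qualify the assistant's role: "The DN4 questionnaire, administered by clinicians, includes 10 items to evaluate neuropathic pain", and "rescue analgesia with IV tramadol (0.5 mg/kg) will be administered as needed".

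On the block itself, section 3.5 says "Following the induction of general anesthesia, the responsible anesthesiologist will independently administer either the PECS I-II or ESP block prior to surgical incision". Sections 2, 3.3 and 3.5 add that the study team does not influence the choice.

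No section mentions masking of the patient, interviewer, outcome assessor or analyst.

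**The concern.** A patient's answer about pain can be affected by how the question is put, when it is probed and how a borderline reply is recorded. If the interviewer knows the block and holds a view about it, these can differ between groups. The 3-month assessment has some room for this: sections 3.5 and 3.6 list DN2 and SF-12 for that call but mention no interview script, and they give no rule for turning the answers into a chronic pain case.

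The comparison is already non-random, because the anaesthesiologist chooses the block. Differential reporting would be a second bias on top of confounding. Section 3.7 plans only unadjusted group comparisons, and no analysis could separate such a bias from a block effect. Enrolling more patients would not remove it either.

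**Working it through.** The plan gives no figure to reproduce here. Section 3.3 sets 40 patients, at least 20 per group, without an effect size or power. The check therefore has two parts.

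**1. Who could be masked, and for which outcome**

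| Outcome | Source according to the plan | Would masking the interviewer protect it? |
|---|---|---|
| Chronic pain incidence (primary) | Telephone interview at 3 months; caller not separately named | Yes; no injection site or chart need be seen |
| NRS and time of first pain | Interview by the study assistant, face to face | Yes, if the block stays concealed |
| DN4 in the first 24 hours | Interview form, but the instrument is described as given by clinicians | Only if whoever administers it is masked |
| Rescue opioid | Tramadol given as needed in routine care | Little; it depends on the patient and care staff |

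The block is given after induction and before incision by someone other than the interviewer, as far as the text shows. Withholding block type from the interview forms changes nothing in care, so the observational design is no obstacle. The limit is physical. The PECS I-II and ESP block protocols in section 3.5 put the injections at the chest wall and axilla in one case and at the back in the other, so a face-to-face interviewer may be able to tell.

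**2. How much a reporting shift could matter**

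Inputs:
- n = 20 per group (section 3.3, taken as 1:1).
- Significance level 0.05 (section 3.7; two-sided assumed).
- Chi-square or Fisher's exact test (section 3.7).
- True incidence 45% in both groups. This is the midpoint of the 40% to 50% that section 2 cites as background, not a design assumption of the plan.
- The size of the reporting shift is an assumption. The documents give none.

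One patient recorded differently moves a group's incidence by 1/20 = 5 points. One patient per group, in opposite directions, turns 45% v 45% (9/20 each) into 50% v 40% (10/20 v 8/20), a spurious difference of 10 points.

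The probability of a significant result is the exact sum

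P(reject) = Σₐ Σ_b Bin(a; 20, p₁) · Bin(b; 20, p₂) · 1[test on a/20 v b/20 significant at 0.05].

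| Reported incidence | Uncorrected chi-square | Fisher's exact |
|---|---|---|
| 45% v 45% (no shift) | 4.4% | 2.2% |
| 47.5% v 42.5% (5 points) | 5.5% | 2.8% |
| 50% v 40% (10 points) | 8.7% | 4.9% |
| 45% v 35% (10 points, one group only) | 9.5% | 5.4% |
| 45% v 25% (20 points, one group only) | 26.9% | 17.9% |

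With the unshifted incidence at 40%, 45% or 50% and one group lowered by 10 points, the range is 8.7% to 10.4% for chi-square and 4.9% to 5.9% for Fisher. A 10-point shift therefore roughly doubles the false-positive rate under either test. Whether it passes the nominal 5% depends on the test.

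For scale, the 95% confidence interval for the difference has half-width 1.96 × √(2 × 0.45 × 0.55 / 20) = 0.308, about 31 points. A 10-point bias is well inside the sampling error of one study of this size, but it is still a shift in the estimate.

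**The case against.** The strongest reply is that the plan is silent and does not describe open assessment. A reader might infer from the silence that the assistant knows the block. The text does not say so, and the person giving the block works independently of the study team. That stands: the supportable statement is that no masking is described.

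A reader might also infer that one unmasked person collects every outcome. The documents do not support this either. DN4 is described as given by clinicians, the 3-month caller is not separately named, and rescue tramadol depends on care staff. Section 3.6 does not say who records the intraoperative details or on which form.

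Next, both groups receive an active block, section 2 describes both as effective, and no hypothesis favours one. NRS, DN2 and SF-12 are also structured patient answers, not assessor ratings. A differential effect is therefore possible but not shown, and its direction is unknown. This limits what can be claimed about size. It does not remove the case for prevention, because a bias of unknown direction cannot be corrected afterwards.

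Finally, masking is not free and may fail at the bedside. That also stands, but it applies mainly to the first 24 hours and not to the telephone call that carries the primary outcome.

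**Conclusion.** The concern holds in limited form. The protocol describes no masking of the interviewer, the primary outcome and the acute pain scores are patient reports obtained by interview, and masking is feasible, most clearly for the 3-month call.

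The size is unknown. The rise from 4.4% to 8.7% (uncorrected chi-square) or from 2.2% to 4.9% (Fisher's exact) rests on an assumed 10-point shift, a 45% background incidence and exactly 20 per group. It would be wrong to read 8.7% as the study's actual error rate: no shift is documented, and with Fisher's exact test the same scenario stays just under 5%.

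This is a cheap improvement to the design. Masking the interviewer would leave the larger problem, confounding by the anaesthesiologist's choice of block, where it is.

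**What to change.** In sections 3.5 and 3.6:

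- Record block type only on the intraoperative sheet, kept from whoever conducts the interviews.
- Use interview forms without the block and a fixed script, linked by study number and joined to block type only at analysis.
- Require masking of the caller for the 3-month telephone interview. Attempt it for the face-to-face interviews in the first 24 hours, and record any unmasking.
- Name who administers DN4 and DN2, so that the masking rule covers the right people.
- If masking is not feasible at some time point, say so and report open assessment as a limitation.

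The cost is one form split in two, a paragraph of text, and someone who does no interviews to hold the block data; the plan does not describe staffing. Masking may fail in the first 24 hours because injection sites and notes can reveal the block. The change does not protect the rescue opioid outcome, which is driven by care, and does not address confounding by block choice.

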### **3.7. Data Analysis**

Normality of numeric data will be assessed using the Shapiro-Wilk test. Data following a normal distribution will be compared between two independent groups using the Student's t-test. Non-normally distributed data will be analyzed using the Mann-Whitney U test. For three-group comparisons, one-way ANOVA will be used if parametric assumptions are met; otherwise, the Kruskal-Wallis H test will be applied. Descriptive statistics will include mean  $\pm$  standard deviation for normally distributed data, or median (minimum–maximum) for non-normal data. Categorical variables will be summarized as counts (percentages), and group comparisons will be performed using chi-square or Fisher's exact test as appropriate. A p-value  $<0.05$  will be considered statistically significant in all analyses.

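### Time of initial pain is a time-to-event variable cut off at 24 hours, but Section 3.7 offers only a t-test or Mann-Whitney test, which on recorded times omit patients who stay pain-free

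*Combined protocol and SAP*

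**What the plan says.** Section 3.5 (Postoperative Pain Control) lists the acute variables. One is an onset time: "Time of initial pain, and whether rescue analgesia was needed within the first 24 hours, will be recorded". NRS is scheduled at 20 minutes, 6 hours and 1 day, with no condition on who is assessed.

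Section 3.6 sets the window: "Postoperative data within the first 24 hours will be collected via face-to-face interviews and entered into the follow-up and DN4 forms".

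Section 3.7 is the whole analysis plan. For numeric data in two groups it gives two tests. The first is: "Data following a normal distribution will be compared between two independent groups using the Student's t-test". The second is: "Non-normally distributed data will be analyzed using the Mann-Whitney U test". It also names ANOVA and Kruskal-Wallis for three groups, and chi-square or Fisher's exact test for categorical data. It names no time-to-event method, no censoring rule and no value or rank for a patient without an onset time. No other section supplies one.

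Section 2 names the outcomes: incidence of chronic pain (primary), and acute pain levels and opioid requirements (secondary). Time of initial pain is not among them.

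**The concern.** A patient with no pain through 24 hours has no onset time to enter. What is known is that onset, if it comes at all, lies beyond 24 hours. That is a censored observation, and neither of the two listed tests can use it as such.

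If the tests are run on the times that exist, the patients who did best leave the comparison. Whether a patient has pain within 24 hours may itself depend on the block, so the remaining groups are selected on something that happened after treatment. If one block keeps more patients pain-free, that benefit disappears from the onset comparison. If the blocks also differ in when pain starts among those who have it, the recorded-only result can point towards the block that leaves more patients in pain.

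**Working it through.** The plan gives no figure on this point, so there is none to reproduce. The check has three steps.

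**1. Which patients have a value.** This follows from Sections 3.5 and 3.6.

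- Pain begins within 24 hours and persists: onset time exists.
- Pain begins within 24 hours and resolves, with NRS = 0 at 1 day: onset time exists.
- No pain through 24 hours: no onset time.

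Only the third kind of patient is lost from a test on recorded times.

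**2. How much this can matter.** From the documents: at least 20 per group and 0.05 significance (Sections 3.3 and 3.7), a 24-hour window (3.6) and the assessment times (3.5). Everything else is assumed: a two-sided test, and the onset distributions and pain-free rates below. There were 4,000 simulated trials per row, so the Monte Carlo standard error is at most √(0.25/4000) = 0.8 percentage points.

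In the rows with medians, onset is exponential and the pain-free proportion at 24 hours is 2^(−24/median):

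- 8 h: 2^(−3) = 12.5%
- 12 h: 2^(−2) = 25%
- 16 h: 2^(−1.5) = 35%
- 24 h: 2^(−1) = 50%

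In the rows with a share in pain, that share is fixed and onset is exponential, truncated at 24 hours. Grouped means that onset is known only to the first assessment at or after it (20 min, 6 h, 24 h).

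| Assumed truth | Pain-free | Recorded-only Mann-Whitney | Log-rank, all patients | Recorded-only, grouped | Log-rank, grouped |
|---|---|---|---|---|---|
| Medians 12 v 12 h (null) | 25% v 25% | 4% | 5% | 5% | 5% |
| Medians 2 v 3 h | under 1% both | 18% | 25% | 15% | 17% |
| Medians 4 v 6 h | 2% v 6% | 15% | 25% | 12% | 19% |
| Medians 8 v 12 h | 13% v 25% | 8% | 21% | 7% | 19% |
| Medians 8 v 16 h | 13% v 35% | 11% | 49% | 9% | 45% |
| Medians 8 v 24 h | 13% v 50% | 15% | 81% | 10% | 78% |
| 95% v 90% in pain, same onset | 5% v 10% | 5% | 8% | 5% | 6% |
| 90% v 60% in pain, same onset | 10% v 40% | 5% | 55% | 5% | 53% |
| 80% v 40% in pain, same onset | 20% v 60% | 5% | 72% | 4% | 72% |
| 90% v 60% in pain, onset medians among them 6.6 v 3.0 h | 10% v 40% | 41% | 26% | 35% | 27% |

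Entries are rejection rates. Section 3.7's own route (Shapiro-Wilk, then t-test or Mann-Whitney) on recorded times changes little: 16% for 8 v 24 h, 5% for 80% v 40%, and 43% for the last row. In the last row the recorded-only test tends to favour the block that leaves more patients in pain, because onset is later among its patients who have pain.

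**3. Whether ranking pain-free patients last in a Mann-Whitney test would do equally well.** It recovers most of the loss in the simple cases (75% for 8 v 24 h, 62% for 80% v 40%), but it is not equivalent to the log-rank test. In the last row of the table it rejects in 8%, against 26% for log-rank. With 95% v 80% in pain and the same onset medians of 6.6 v 3.0 h, it rejects in 12% against 6%. Nearly all of its rejections there (11.8% against 0.6% the other way, in a separate run) favour the block that leaves more patients in pain.

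**The case against.** **Section 3.7 does not say that pain-free patients are dropped.** This stands. A reader might infer a planned subset comparison, but the text is only silent. The follow-up form is not in the documents and may code absence of pain. Even so, Section 3.7 does not say how such a code enters a t-test or Mann-Whitney test, and step 3 shows that two reasonable choices can disagree.

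**Onset is ancillary.** This also stands. A reader might infer that the main results are at risk, and the documents do not support that. NRS and rescue use are recorded without a pain condition, and the 3-month assessment is separate. If pain persists to an assessment once begun (an assumption), a contrast of 80% v 40% in pain would also show as NRS above 0 against 0. Fisher's test, already in Section 3.7, has 65% power for that with 20 per group. The signal would be missed in one variable, not in the study.

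**The large effects need large gaps.** The same-onset rows with a big loss assume gaps of 30 to 40 points in pain-free rates between two active blocks. No figure in the documents supports these, and at 95% v 90% almost nothing is lost.

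**The last table row is not a false positive.** Correct. Onset among patients with pain really is later there by construction. The recorded-only test answers a different question, which could be misread as a benefit of the block.

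**DN4.** The plan says "If NRS >0, the DN4 (Douleur Neuropathique 4) questionnaire will be administered", and one might read this as the same fault. It is an ordinary skip pattern. A patient with NRS = 0 is naturally counted as not positive, and counts with percentages already allow a denominator of all patients. Only a reporting note follows.

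**Conclusion.** The concern holds as a minor one, for time of initial pain only. The variable is censored at 24 hours, the listed two-group tests cannot use censored values, and a log-rank test on all patients is a better method at little cost.

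The size cannot be fixed from the documents. It is negligible if nearly all patients have pain within 24 hours. Under the assumed scenarios it reaches 15% against 81% rejection when 13% v 50% stay pain-free. These figures rest on 20 per group, a two-sided 0.05 test, and exponential onset or fixed shares in pain. They are illustrations, not forecasts. The advantage remains when onset is known only to the scheduled assessments.

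**What to change.** Add to Section 3.7:

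1. Time of initial pain is measured from a stated origin, such as end of surgery, and is analysed in all patients by Kaplan-Meier curves and a log-rank test.
2. Patients who report no pain through 24 hours are censored at 24 hours, or at their last completed assessment if that is earlier. Patients whose pain began and later resolved count as events.
3. If onset is known only to the scheduled assessments, say so and use the grouped times.
4. The number pain-free in each group is reported alongside.

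Do not offer a Mann-Whitney test with pain-free patients ranked last as an interchangeable alternative.

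As a reporting note only, give DN4 ≥4 at 20 minutes, 6 hours and 1 day as a proportion of all patients assessed at that time, with NRS = 0 counted as negative.

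The cost is a few sentences and a little more analysis work. The form needs the time origin, the last completed assessment, and a mark that separates NRS = 0 from a missed assessment. Onset times may remain coarse. Patient care does not change.

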#### **3.3 Study Population, Sample Size, and Study Groups**

Following approval by the Hacettepe University Ethical Committee, patients aged 18 to 65 years, classified as ASA physical status I-II, and scheduled to undergo elective modified radical mastectomy or simple mastectomy with sentinel/axillary lymph node dissection under general anesthesia at Hacettepe University Hospitals between April 15 and May 15, 2024, will be included. Patients must have already been scheduled to receive either an ESP or PECS I-II block for postoperative pain management independently of the study. A total of 40 patients will be enrolled, with 20 in each group at least. Patients with coagulation disorders, allergies to local anesthetics, obesity ( $BMI > 35 \text{ kg/m}^2$ ), infection at the injection site, pre-existing neurological deficits, or unwillingness to participate, as well as those with failed blocks, will be excluded. The decision to perform blocks is made by the responsible anesthesiologist and will not be influenced by the study team.

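### Opioid requirement is a stated secondary outcome, but the only rescue item named is yes/no within 24 hours; tramadol doses and times should be taken from the chart unless the follow-up form already holds them.

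*Combined protocol and SAP*

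**What the plan says.** Section 2 gives the secondary aim as to "assess the impact of these blocks on acute postoperative pain levels and opioid requirements". Section 3.5, under Postoperative Pain Control, describes routine paracetamol and adds that "rescue analgesia with IV tramadol (0.5 mg/kg) will be administered as needed". Of this rescue treatment, the same section says only that "whether rescue analgesia was needed within the first 24 hours, will be recorded". It also records when pain first appears, but that is the onset of pain, not the time of a rescue dose.

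Section 3.6 gives the data source: "Postoperative data within the first 24 hours will be collected via face-to-face interviews and entered into the follow-up and DN4 forms". The follow-up form is not reproduced. The other items listed there are "Patient demographic data (ASA score, age, sex, weight, height, BMI, comorbidities) and intraoperative details will be recorded". These include weight but no postoperative drug use.

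Section 3.7 names no opioid endpoint. It sends categorical variables to chi-square or Fisher's exact test, and for skewed numeric variables says: "Non-normally distributed data will be analyzed using the Mann-Whitney U test". On sample size, section 3.3 says: "A total of 40 patients will be enrolled, with 20 in each group at least".

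**The concern.** How much opioid a patient required is naturally an amount. The item named in the text records only whether any was given. Tramadol is dosed by weight and given on demand. If a patient can receive it more than once, which is a fair reading although the protocol does not say so, yes/no puts a patient who had one dose in the same category as a patient who had several. Two blocks with the same share of patients needing any rescue but quite different totals would then appear equal on this half of the secondary outcome. The lost information cannot be rebuilt from the named items, because weight is recorded but the number of doses is not.

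There is also an effect on the other half of that outcome. The pain scores at 6 hours and 1 day may be taken after rescue. A low score after several doses means something different from a low score after none, and without amount and time the two cannot be told apart. Finally, an interview is a weak source for drug amounts, since a patient may not know which drug was given or how much.

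**Working it through.** **Text check.** Setting sections 2, 3.5, 3.6 and 3.7 side by side, the outcome is opioid requirement, the recorded variable is binary, the named source is the interview, and no analysis of an opioid amount is described. The intraoperative details in section 3.6 are unspecified and would not cover postoperative rescue.

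**No figure to reproduce.** The protocol gives 40 patients, at least 20 per group, with no power, effect size, rescue rate or dose distribution. The calculation below therefore shows scale only.

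**Inputs.** From the documents: n = 20 per group (3.3), significance level 0.05 (3.7), 0.5 mg/kg per dose (3.5). Assumed: a two-sided test and every rescue rate and dose count.

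**Why a dose count can stand in for mg/kg.** If each dose is given as written, total mg/kg = 0.5 × number of doses. The ranks, and so the Mann-Whitney result, are the same for both. In milligrams, assumed weights of 50 to 90 kg give 0.5 × 50 = 25 mg to 0.5 × 90 = 45 mg per dose.

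**Method.** With Poisson mean m, the share needing any rescue is 1 − exp(−m). For means 2 v 1 this is 1 − exp(−2) = 0.86 against 1 − exp(−1) = 0.63. Yes/no power sums the two binomial probabilities over all 2×2 tables with p < 0.05. Mann-Whitney power comes from 20,000 simulated trials per row, using the normal approximation with tie and continuity corrections.

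| Mean doses per patient | Mann-Whitney on count | Yes/no, uncorrected chi-square | Yes/no, Fisher |
|---|---|---|---|
| 0.5 v 0.2 | 33% | 33% | 22% |
| 0.7 v 0.2 | 62% | 60% | 48% |
| 1 v 0.5 | 40% | 30% | 21% |
| 1.5 v 0.75 | 56% | 39% | 28% |
| 2 v 1 | 69% | 41% | 29% |
| 3 v 1.5 | 85% | 36% | 23% |

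Two bounding cases:

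- Every user takes exactly one dose, with 80% v 40% needing rescue: 73% on the count, against 75% (chi-square) and 65% (Fisher). The count adds nothing over chi-square.
- 80% need rescue in both groups, and users take 1 + Poisson doses averaging 3 v 1.5: 65% on the count, against 5% and 2%. Here yes/no carries no signal by construction, so this is the extreme.

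**Reading.** The gain grows with the number of doses per patient. As use rises, most patients in both groups become a yes and the binary contrast shrinks: for 3 v 1.5 it is 1 − exp(−3) = 0.95 against 1 − exp(−1.5) = 0.78.

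**The case against.** The strongest reply is that nothing here contradicts itself. Section 2 speaks of requirement, not consumption or milligrams. Whether a patient needed rescue is a legitimate reading, and section 3.7 has a test for it. That stands: this is a weak choice of measure, not an inconsistency.

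Second, the follow-up form is not reproduced and may already hold dose and time. That also stands, so the request is conditional. Even if the form holds them, the protocol should name the outcome variable.

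Third, repeat dosing is not stated, and rescue may be infrequent after a block with scheduled paracetamol. With mostly single-dose users, Mann-Whitney is marginally below chi-square: about 61% v 62% when 40% v 10% need rescue and users average 1.2 doses, and about 74% v 75% when 60% v 20% need it and users average 1.3. It still beats Fisher (65% in the second case). This limits the expected gain in power. It does not remove the case for recording amounts, because the documents give no basis for assuming single doses.

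Fourth, if every dose is exactly 0.5 mg/kg, a simple dose count would serve as well. True, but recording each dose also covers any that depart from the written amount.

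**Conclusion.** The concern holds. Opioid requirement is a stated secondary outcome, and the text names only a yes/no item for it, from which the amount used cannot be derived. The possible loss runs from none against chi-square, when users take one dose each, through 69% v 41% or 29% at means of 2 v 1, to 65% v 5% or 2% when only the number of doses differs. All these figures rest on assumed rates and dose distributions, 20 per group and a two-sided 0.05 level. The point also assumes that doses can repeat and that the unseen follow-up form does not already capture them. It affects half of the secondary outcome and the interpretation of the 6-hour and 1-day pain scores, but not the primary outcome. It should be changed because the remedy is cheap, though the study does not depend on it.

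**What to change.** 1. In sections 3.5 and 3.6, state that each tramadol dose (mg) and its time in the first 24 hours will be copied from the medication chart. If the follow-up form already captures this, confirm it and say so.
2. In section 3.7, define the opioid-requirement outcome as total tramadol over 24 hours in mg/kg, with zero for patients given none, using the weight already recorded. Name Mann-Whitney as the test; it is already in that section.
3. Keep rescue yes/no as a supporting summary, and report both measures beside the 6-hour and 1-day pain scores.

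The cost is a chart look-up of a few minutes for each of about 40 patients, one form field and one sentence in section 3.7. If the charts hold dose and time, which is an assumption, they can be read after the event. How rescue is given does not change, so the study stays observational. The downside is little or no gain in power if most users receive a single dose.
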